3.4 Pharmacokinetic Evaluations

Collection of samples for pharmacokinetics and anti-therapeutic antibodies is not included in this extension study.

3.5 In Vivo Biomarker and Exploratory Research

Not applicable.

4 INVESTIGATIONAL PLAN

4.1 Overall Study Design and Plan

This is a phase 2, multicenter, long-term, rollover follow-up extension study. It will be conducted in ~20 sites in the same countries as the rovalpituzumab tesirine parent studies; potentially including, but not limited to, Canada, France, Latvia, Spain, the United Kingdom, and the United States. More study sites and countries may be included as other rovalpituzumab tesirine parent studies complete their primary analyses and close.

The schedule of assessments will depend on whether subjects enter the study in post-treatment follow-up or receiving ongoing rovalpituzumab tesirine treatment from the parent study.

[figure not shown]
This extension study includes 2 Study Arms:

- Arm A: Subjects who enter the extension study while in post-treatment follow-up. This arm
 includes optional rovalpituzumab tesirine retreatment for those who qualify. Most subjects
 from all studies will be in this arm. These parent studies include, but are not limited to,
 Study SCRX001-002, Study SCRX001-004, Study SCRX001-006, Study SCRX001-007, and
 Study M16-289.
- Arm B: Subjects who enter the extension study while receiving ongoing rovalpituzumab tesirine treatment in the parent study (e.g., Study SCRX001-007).

Study specifics for Arms A and B are presented in Figure 1.

Figure 1. Study Schematic

D/C = Study discontinuation; Tx = Treatment

4.2 Discussion of Study Design

Choice of Control Group

There is no control group in this extension study.

Appropriateness of Measurements

Standard clinical and laboratory procedures will be utilized in this study. All efficacy measurements in this study are standard for assessing disease activity in subjects with SCLC and other indications from parent rovalpituzumab tesirine studies (e.g., Study SCRX001-006).

Suitability of Subject Population

These are all subjects who were enrolled in rovalpituzumab tesirine treatment studies, but have not yet reached 1 or more endpoints in the parent study at the time of primary analyses. In addition, subjects who were eligible for retreatment based on the criteria written in the parent study will have that opportunity in this study.

All subjects must have received at least 1 dose of rovalpituzumab tesirine in the parent study. In order to receive optional retreatment in Arm A, subjects must meet the below eligibility criteria in Section 5.1.

Selection of Doses in the Study

Subjects who receive treatment in this study will receive rovalpituzumab tesirine at a dose of 0.3 mg/kg on Day 1 of every 6 week treatment cycle. If a subject previously required a dose reduction during the parent rovalpituzumab tesirine study, then that reduced dose will be administered for those with ongoing treatment or those electing retreatment. Dose reductions may also occur during treatment or retreatment. If a subject requires a dose reduction, either in the parent rovalpituzumab tesirine study or this extension study, dose re-escalation is not allowed.

5 STUDY ACTIVITIES

5.1 Eligibility Criteria

Study Entry Criteria

For both Arms A and B; the eligibility criteria are that a subject has enrolled, participated in, and received at least 1 dose of rovalpituzumab tesirine in a parent study.

Arm A Optional Retreatment Criteria

Additional eligibility criterion for Arm A is that subjects who discontinued the study drug in the parent study have completed the treatment emergent AE reporting window (e.g., 30 days post last dose for Study SCRX001-002).

Subjects who elect optional retreatment in Arm A must meet all of the following eligibility criteria before receiving rovalpituzumab tesirine retreatment. Prior to providing retreatment to subjects, study investigators should consult with the AbbVie Medical Monitor.

Demographic and Laboratory Assessments

- 1. Tolerated their initial 2 doses of rovalpituzumab tesirine
- 2. Achieved clinical benefit from rovalpituzumab tesirine, defined as stable disease or better, and is determined that the subject would potentially benefit from additional treatment

Achieved clinical benefit as defined by stable disease or better and experienced radiographic disease progression at least 12 weeks after last dose of rovalpituzumab tesirine per RECIST 1.1

- 3. Received no other systemic anti-cancer therapy after rovalpituzumab tesirine treatment
- 4. Eastern Cooperative Oncology Group (ECOG) performance status of 0 or 1. See the Operations Manual, Appendix B for conversion of performance status using Karnofsky scales, if applicable
- 5. Minimum life expectancy of at least 12 weeks

- 6. Laboratory values meeting the following criteria within the screening period prior to the first dose of study drug:
 - Absolute neutrophil count (ANC) ≥ 1,500/μL;
 - Platelet count ≥ 75,000/μL;
 - Hemoglobin ≥ 8.0 g/dL;
 - Serum total bilirubin $\leq 1.5 \times$ upper limit of normal (ULN) or $\leq 3 \times$ ULN for subjects with Gilbert's disease;
 - Serum alanine aminotransferase (ALT) and aspartate aminotransferase (AST) ≤ 2.5 × ULN (≤ 5 × ULN if evidence of hepatic involvement by malignant disease);
 - Serum creatinine ≤ 1.5 × ULN or estimated glomerular filtration rate (eGFR)
 ≥ 30 mL/min/1.73 m² as calculated by the 4-variable Modification of Diet in Renal Disease study equation (GFR (mL/min/1.73 m²) = 175 × (serum creatinine [mg/dL])-1.154 × (age [years])-0.203 × 0.742 (if female) × 1.212 (if African American).³

Disease Activity

- 7. Recovery to Grade 1 or baseline of any clinically significant rovalpituzumab tesirine related toxicity (excluding alopecia) prior to initiation of study drug
- 8. In subjects with central nervous system (CNS) metastases, documentation of stable or improved status based on brain imaging for at least 2 weeks after completion of definitive treatment and within 2 weeks prior to initiation of retreatment, off or on a stable dose of corticosteroids. (Note: Definitive treatment may include surgical resection, whole brain irradiation, and/or stereotactic radiation therapy)

Contraception

- 9. A negative urine pregnancy test for all female subjects (except post-menopausal) at the Screening Visit and a negative urine pregnancy test for all female subjects (except postmenopausal) at baseline prior to the first dose of study drug
- 10. If female, is not pregnant, breastfeeding, or considering becoming pregnant during the study or for approximately 6 months after the last dose of study drug
- 11. Females of childbearing potential must have a negative urine pregnancy test result within 7 days prior to the first dose of study drug. Females of non-childbearing potential are those who are postmenopausal greater than 1 year or who have had a bilateral tubal ligation or hysterectomy
- 12. Females of childbearing potential and males who have partners of childbearing potential must agree to use an effective contraception method (see Section 5.2) during the study and for 6 months following the last dose of study drug
- 13. If male, is not considering fathering a child or donating sperm during the study or for approximately 6 months after the last dose of study drug

5.2 Contraception Recommendations

Contraception Requirements for Females

No contraception is required for female subjects of non-childbearing potential, defined as those who are postmenopausal for greater than 1 year or who have had a bilateral tubal ligation or hysterectomy. Postmenopausal is defined as:

- Age > 55 years with no menses for 12 or more months without an alternative medical cause
- Age ≤ 55 years with no menses for 12 or more months without an alternative medical cause AND a follicle-stimulating hormone (FSH) level > 40 IU/L
- OR Permanently surgically sterile (bilateral oophorectomy, bilateral salpingectomy or hysterectomy)

Females of childbearing potential must agree to practice at least one of the following methods of birth control at enrollment (or earlier) through at least 6 months after the last dose of study drug. Effective birth control includes:

- Combined (estrogen and progestogen containing) hormonal birth control (oral, intravaginal, transdermal) associated with inhibition of ovulation initiated at least 1 month prior to enrollment
- Progestogen-only hormonal contraception (oral, injectable, implantable) associated with inhibition of ovulation initiated at least 1 month prior to study Baseline Day 1
- Bilateral tubal occlusion/ligation (Note: Bilateral tubal occlusion via hysteroscopy [i.e., Essure] is acceptable provided a hysterosalpingogram has confirmed success of the procedure)
- Intrauterine device
- Intrauterine hormone-releasing system
- Vasectomized sexual partner(s): provided the vasectomized partner has received medical assessment of the surgical success and is the sole sexual partner of the trial participant
- True abstinence: Refraining from heterosexual intercourse when this is in line with the preferred and usual lifestyle of the subject (Note: periodic abstinence [e.g., calendar, ovulation, symptothermal, post-ovulation methods] and withdrawal are not acceptable)

Contraception Requirements for Males

No contraception is required for male subjects who are surgically sterile (vasectomy with medical assessment confirming surgical success) or who have a female partner that is postmenopausal or permanently sterile (bilateral oophorectomy, bilateral salpingectomy or hysterectomy).

If a male subject is sexually active with female partner(s) of childbearing potential, he must agree to use condoms until 6 months after the last dose of investigational product. In addition, for such subjects:

- Female partner(s) must use at least one of the contraceptive measures (as defined in the protocol for female study subjects of childbearing potential), or
- Subject must practice true abstinence, defined as refraining from heterosexual intercourse
 when this is in line with the preferred and usual lifestyle of the subject. (Note: Periodic
 abstinence [e.g., calendar, ovulation, symptothermal, post-ovulation methods] and withdrawal
 are not acceptable)

Further, male subjects must agree not to donate sperm from enrollment through 6 months after the last dose of investigational product.

5.3 Prohibited Medications and Therapy

Not applicable.

5.4 Prior and Concomitant Therapy

For subjects who will receive rovalpituzumab tesirine in this extension study, dexamethasone 8 mg twice daily (BID) or an equivalent corticosteroid will be administered around the time of dosing (Day –1, 1, and 2).

Any medication or vaccine (including over the counter or prescription medicines, vitamins and/or herbal supplements) that the subject is receiving at the time of enrollment or receives during the study must be recorded through the AE reporting window (70 days after last dose). All anti-cancer medication or treatments will be collected for the duration of the study.

5.5 Withdrawal of Subjects and Discontinuation of Study

A subject may voluntarily withdraw or be withdrawn from the study at any time for reasons including, but not limited to, the following:

- The subject withdraws consent for participation in the study;
- The Investigator believes it is in the best interest of the subject;
- Subject is significantly non-compliant with study procedures, which would put the subject at risk for continued participation;
- Subject is lost to follow-up or dies;
- The study is terminated by the sponsor.

Subjects who withdraw or discontinue prematurely from the study will not be replaced.

For subjects to be considered lost to follow-up, reasonable attempts must be made to obtain information on the final status of the subject. At a minimum, 2 telephone calls must be made and 1 certified letter must be sent and documented in the subject's source documentation.

A subject can:

- withdraw participation in clinic visits, but be included in the follow-up for overall survival by phone call,
- withdraw participation in the overall survival follow-up by phone call, or
- withdraw participation in both clinic visits and overall survival follow-up by phone call

AbbVie may terminate this study prematurely, either in its entirety or at any site. The Investigator may also stop the study at his/her site if he/she has safety concerns. If AbbVie terminates the study for safety reasons, AbbVie will promptly notify the Investigator.

Follow-up procedures and survival information collection are described below in Section 5.6.

5.6 Follow-Up for Subject Withdrawal from Study

To minimize missing data for efficacy and safety assessments, subjects who prematurely discontinue study drug treatment should continue to be followed for all regularly scheduled visits, unless subjects have decided to discontinue the study participation entirely (withdrawal of informed consent). Subjects should be advised on the continued scientific importance of their data even if they discontinue treatment with study drug early.

If a subject prematurely discontinues study participation (withdrawal of informed consent), the procedures outlined for the Premature Termination Follow Up (PTFU visit) should be completed as soon as possible, preferably within 2 weeks. All attempts must be made to determine the date of the last study drug dose and the primary reason for discontinuation of study drug or study participation. The information will be recorded on the appropriate electronic Case Report Form (eCRF) page. However, these procedures should not interfere with the initiation of any new treatments or therapeutic modalities that the Investigator feels are necessary to treat the subject's condition. Following discontinuation of study drug, the subject will be treated in accordance with the Investigator's best clinical judgment, irrespective of whether or not the subject decides to continue participation in the study.

Subjects no longer undergoing clinical assessments will have survival information collected approximately every 6 weeks until the endpoint of death, the subject becomes lost to follow-up or withdraws consent, or termination of the study by AbbVie, whichever occurs first. In addition, if the subject is willing, a 70-day follow-up phone call after the last dose of study drug may be completed to ensure all treatment-emergent AEs/SAEs have been resolved.

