3.3 Safety Evaluations

Safety evaluations include adverse event monitoring, physical examinations, echocardiography, vital sign measurements, performance status, and clinical laboratory testing. Adverse events (AEs) will be collected from the time of enrollment until the end of the study. For subjects receiving treatment/retreatment in this study, all AEs regardless of seriousness or causality, will be reported through 70 days after the last dose of treatment. Only treatment-related serious adverse events (SAEs) will be collected post 70 days of the last dose of rovalpituzumab tesirine received in the study. In those subjects in Arm A who are not receiving treatment, only treatment-related SAEs will be collected. The AE reporting windows are described below in the schema.

Adverse Event Reporting

Last rovalpituzumab tesirine dose refers to the last dose received by the subject in either the parent study (Arm A, No Retreatment) or this extension study (Arm A Retreatment or Arm B).

Further details on AE reporting are provided in Section 6.1 and the Operations Manual, Section 4. For statistical analysis provided for study disclosure, refer to Section 7.5.

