7.5 Statistical Analyses for Safety

Adverse events will be coded and summarized by system organ class and preferred term (and severity) according to the Medical Dictionary for Regulatory Activities (MedDRA) version 20.1 or higher. Clinical toxicity grades modified from the NCI CTCAE version 4.0 will be used in the grading of AEs and laboratory abnormalities that are reported as AEs.

No safety analyses will be performed. A listing of data for subjects experiencing AEs will be provided. Laboratory measurements collected on the eCRF will also be listed.

For study disclosure, the following safety data will be summarized:

- For Arm A: Serious adverse events related to treatment will be summarized.
- For Arm B and those who are retreated on Arm A: AEs from enrollment to 70 days after the last dose and SAEs related to rovalpituzumab tesirine from 71 days after the last dose until the end of study will be summarized.

Definitions of AEs are provided in Section 6.1 and the Operations Manual, Section 4.

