□ INTERVIEW	 Adverse events Concomitant medications Fluid retention questionnaire (see example in Appendix C)^a 				
EXAMS	Vital signs Physical exam				
∠ CENTRAL LABS	Complete blood count Urinalysis Chemistries				
subject and NOTES: Every third	a. Fluid retention questionnaires need to be collected from and discussed with the subject and new questionnaires provided to the subject.				
Fluid retention questionnaire follow-up phone call					
TREATMENT CYCLE: DAY 29 ± 3 DAYS					
Adverse events Fluid retention questionnaire (see example in Appendix C) ^a Concomitant medications					
* EXAMS	Physical exam Vital signs				
▲ CENTRAL LABS	Complete blood count Urinalysis Chemistries				
 a. Fluid retention questionnaires need to be collected from and discussed with the subject and a new questionnaire provided to the subject. NOTES: Every third cycle excludes rovalpituzumab tesirine and dexamethasone treatment. 					

TREATMENT	CYCLE:	DAY	36 + 2	Day	/S
------------------	--------	-----	--------	-----	----

□ INTERVIEW •	Fluid retention questionnaire follow-up phone call
---------------	--

POST-CYCLE RESPONSE ASSESSMENT: WITHIN 7 DAYS OF NEXT DOSE OF STUDY DRUG:

□ INTERVIEW	•	Fluid retention questionnaire (see example in Appendix C) ^a	•	Adverse events Concomitant medications
* EXAMS	10	Physical exam		
5 LOCAL LABS & IMAGING	•	Disease/response assessment ^b		

- a. Fluid retention questionnaires need to be collected from and discussed with the subject and new questionnaires provided to the subject.
- b. Response assessment and brain MRI (if clinically indicated) to be performed only in subjects who have not yet experienced radiographic disease progression.
- NOTE: This appointment is conducted at a clinic visit on Days 35 42 of each cycle and is to be conducted if the subject is continuing with royalpituzumab tesirine treatment.

END OF TREATMENT: 42 DAYS ± 3 DAYS AFTER LAST DOSE (IF SUBJECT IS STOPPING TREATMENT)

□ INTERVIEW	 Fluid retention questionnaire (see example in Appendix C)^a 	Adverse eventsConcomitant medications
* EXAM	 Physical examination 	 Vital signs
5 LOCAL LABS & IMAGING	Pregnancy test (urine)	 Disease/response assessment^b
A CENTRAL LAB	Complete blood countChemistries	Coagulation testsUrinalysis

- a. Fluid retention questionnaires need to be collected from and discussed with the subject.

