- b. Response assessment and brain MRI (if clinically indicated) to be performed only in subjects who have not yet experienced radiographic disease progression.
- NOTES: The End of Treatment (EOT) assessment is conducted at a clinic visit. This visit should occur 42 days ± 3 days after last dose, or within 7 days of documentation of the decision to discontinue treatment, whichever is later.

LONG TERM FOLLOW-UP VISITS: EVERY 6 WEEKS ± 1 WEEK UNTIL 24 WEEKS AFTER FIRST ROVALPITUZUMAB TESIRINE DOSE, THEN EVERY 12 WEEKS ± 1 WEEK (FOR POST-TREATMENT FOLLOW-UP) OR EVERY 12 WEEKS ± 2 WEEKS (FOR SURVIVAL FOLLOW-UP)

□ INTERVIEW^a

- Adverse events
 - Concomitant medications
- Survival status/Death (date and cause)

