5 LOCAL LABS & IMAGING

- Disease/response assessment^b
- a. Visit can be a phone call for subjects who have already experienced disease progression.
- b. Response assessment and brain MRI (if clinically indicated) to be performed only in subjects who have not yet experienced radiographic disease progression.

NOTE Post-Treatment Follow-Up: For all subjects who discontinue study treatment for reasons other than disease progression, the first follow-up visit will occur at 6 weeks (± 1 week) after the last Response Assessment, then every 6 weeks (± 1 week) until 24 weeks after first dose of rovalpituzumab tesirine, then every 12 weeks (± 1 week) until disease progression or initiation of new anti-cancer therapy, whichever occurs first.

Survival Follow-Up: After disease progression or if subjects stop treatment and decline further study radiographic assessments prior to the endpoint of disease progression, subjects will be followed for subsequent anti-cancer therapies (dates and responses), as well as survival status, every 6 weeks* (± 1 week) until 24 weeks after first dose of rovalpituzumab tesirine, then every 12 weeks (± 2 weeks) until the endpoint of death, the subject becomes lost to follow-up or withdraws consent, or termination of the study by AbbVie, whichever occurs first (*or as requested by AbbVie). If the subject withdraws from study follow-up, the study staff may use a public information source (such as county records) to obtain information about survival status only, as appropriate per local regulations.

END OF STUDY VISIT

- Adverse event
- · Concomitant medications
- Disease/response assessment^b
- Survival status/Death (date and cause)
- Visit can be a phone call for subjects who have already experienced disease progression.
- b. Response assessment and brain MRI (if clinically indicated) to be performed only in subjects who have not yet experienced radiographic disease progression.

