4 SAFETY MANUAL

4.1 Methods and Timing of Safety Assessment

Adverse Event Reporting in Arm A and B Subjects who Receive Treatment or Retreatment in This Study

Within the 70 Day Follow-Up Period

Treatment-emergent adverse events (TEAEs) and treatment emergent serious adverse events (SAEs) will be collected; TEAEs and treatment emergent SAEs are defined as those that occur or worsen on or after the first dose of study drug until 70 days after the last dose of study drug.

After the 70 Day Follow-Up Period

All SAEs that occur after the safety reporting period that are considered study drug-related in the opinion of the Investigator should also be reported.

Adverse Event Reporting in Arm A subjects who do not Receive Treatment or Retreatment in This Study

All SAEs that are considered study drug-related in the opinion of the Investigator should be reported.

Deaths due to Cancer Progression

[figure not shown]
Deaths that occur during the protocol specified AE/SAE reporting period (Section 2) that are more likely related to disease progression will therefore be considered as an expected AE and will not be subject to expedited reporting. After the AE reporting period, deaths attributed to progression of disease under study should not be recorded on the AE eCRF, but on the Survival Death eCRF.

Death should be considered an outcome and not a distinct event. The event or condition that caused or contributed to the fatal outcome should be recorded as the single medical concept on the AE eCRF. Generally, only 1 such event should be reported. The term "sudden death" should only be used for the occurrence of an abrupt and unexpected death due to presumed cardiac causes in a subject with or without pre-existing heart disease, within 1 hour of the onset of acute symptoms or, in the case of an unwitnessed death, within 24 hours after the subject was last seen alive and stable. If the cause of death is unknown and cannot be ascertained at the time of reporting, "unexplained death" should be recorded on the AE eCRF. If the cause of death later becomes available (e.g., after autopsy), "unexplained death" should be replaced by the established cause of death.

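### With End of Treatment at day 42 ± 3, no contact is scheduled before the adverse event window closes at day 70, and the only day-70 call is optional and unscheduled

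*Combined protocol and SAP*

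**What the plan says.** **The window.** For subjects treated or retreated in this study, protocol Section 3.3 states that "all AEs regardless of seriousness or causality, will be reported through 70 days after the last dose of treatment". Operations Manual Section 4.1 defines treatment-emergent events as "those that occur or worsen on or after the first dose of study drug until 70 days after the last dose of study drug". Section 7.5 builds the disclosure summary for Arm B and retreated Arm A subjects on "AEs from enrollment to 70 days after the last dose"; from day 71 only related serious events count. Section 5.4 records concomitant medication to the same day 70.

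**The visits.** Operations Manual Section 2.3 lists "END OF TREATMENT: 42 DAYS ± 3 DAYS AFTER LAST DOSE", with a note that moves the visit later where needed: "or within 7 days of documentation of the decision to discontinue treatment, whichever is later". For subjects who stop for a reason other than progression, "the first follow-up visit will occur at 6 weeks (± 1 week) after the last Response Assessment". AEs and concomitant medication are on the checklist for that visit. For survival follow-up, the same section moves from 6-weekly contact, once 24 weeks have passed since first dose, to a wider interval: "then every 12 weeks (± 2 weeks) until the endpoint of death". Protocol Section 5.6 instead has survival information collected about every 6 weeks, with no change at 24 weeks.

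**The day-70 contact.** It appears only in Section 5.6, directly after the sentence on subjects who have stopped clinical assessments. If the subject is willing, "a 70-day follow-up phone call after the last dose of study drug may be completed". Its stated purpose is to confirm that treatment-emergent events have resolved. Neither Appendix D nor Operations Manual Section 2.3 lists it.

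**The concern.** The plan fixes the end of AE collection at day 70 but requires no contact at or near that day. Subjects still in scheduled follow-up are not clearly covered by the call at all, because Section 5.6 frames it for those who have left clinical assessments.

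This matters because the study has no efficacy objectives or endpoints (Section 3.2), so the safety summary for disclosure is its main planned aggregate result. Day 70 is also a sharp boundary in that summary. A non-serious or unrelated event with onset on day 68 counts; the same event on day 72 does not. When the first question is asked after the window has closed, both the event and its onset date may have to be reconstructed.

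The documents themselves treat this period as one of continuing risk. Section 6.3 asks for effusion symptoms to be monitored after treatment and for edema to be monitored in follow-up. Yet the fluid retention questionnaires end at the End of Treatment visit (Operations Manual Section 3.9).

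**Working it through.** The documents state no figure for this gap, so there is none to reproduce. The check is visit-day arithmetic, with days counted from the last dose.

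**Inputs**
- Window closes: day 70 (Sections 3.3 and 7.5; Operations Manual Section 4.1).
- End of Treatment: E = 42, range 39 to 45 (Operations Manual Section 2.3).
- First post-treatment visit: 6 weeks ± 1 week (42 ± 7 days) after the last Response Assessment (same section). End of Treatment includes a response assessment for subjects who have not progressed.
- Cycle length: 42 days (Operations Manual Section 6.1).

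**Step 1: length of the gap.** Gap = 70 − E; share of the post-last-dose period = gap / 70.
- E = 39: 31 days, 31/70 = 44.3%.
- E = 42: 28 days, 28/70 = 40.0%.
- E = 45: 25 days, 25/70 = 35.7%.

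**Step 2: share of the whole treatment-emergent window.** For a two-dose retreatment the window is 42 + 70 = 112 days. With E = 42, 28/112 = 25.0%.

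**Step 3: next visit, stopped without progression.** 42 + 42 = day 84. With ± 7 days this is 77 to 91. Adding the End of Treatment window gives 39 + 35 = 74 to 45 + 49 = 94. All fall after day 70. Even if the last Response Assessment were a day-35 post-cycle visit and follow-up came a week early, the visit would be at 35 + 35 = day 70, not before it. At a day-84 visit, events from the gap are 84 − 70 = 14 to 84 − 42 = 42 days old.

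**Step 4: next contact in survival follow-up.** If the Section 5.6 interval is counted from a day-42 End of Treatment (an assumption), contact is at 42 + 42 = day 84. The Operations Manual interval after 24 weeks has no stated starting point. Counted from End of Treatment, it gives a date well beyond day 84. Counted from first dose, it depends on each subject's dosing dates and could fall in the gap only by coincidence. The date therefore cannot be fixed from the documents.

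**Step 5: exceptions.**
- The omitted third cycle in Arm B keeps its visits and calls. An Arm B subject who goes through it before stopping has contacts at about days 42, 43, 48 (call), 56, 63 (call) and 70.
- A late decision to stop moves End of Treatment. A decision on day 56 allows a visit up to 56 + 7 = 63 (gap 7 days); a decision on day 63 allows a visit up to day 70 (gap 0).

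**Step 6: effect of a required call.** A contact on day 70 leaves no part of the window unasked when it closes. The longest lag, for an event just after a day-42 End of Treatment, falls from 42 days to 70 − 42 = 28 days, or 77 − 42 = 35 days if the call is made a week late.

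**The case against.** The case against has real weight.

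- **The period is not lost.** The follow-up visit at about day 84 lists AEs and concomitant medication, so it can pick up events to day 70. Section 6.1 requires routine AE monitoring throughout the study, and serious events are reportable within 24 hours of the site becoming aware. This stands, and it limits the point to late collection. But routine monitoring sets no contact date, and the 24-hour clock starts only once the site knows.
- **The call is optional for a reason.** Section 5.6 concerns withdrawal, where a subject's willingness is a natural condition. That explains the wording there, but leaves subjects still in follow-up without a day-70 contact.
- **The gap is not universal.** The exceptions in Step 5 stand. A two-dose retreatment has no omitted cycle to fill the gap, and its End of Treatment moves only if the decision to stop is late.
- **The output is descriptive.** There is no hypothesis, no control group and no formal safety analysis, so no inference is put at risk. This limits severity.

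Some stronger readings are tempting but unsupported. A reader might infer that subjects who progressed wait a full 12 weeks after End of Treatment for their next contact. That needs a starting point the documents do not give and sets aside the interval of about 6 weeks in Section 5.6. A reader might go on to infer that many die before being asked. The documents give no survival figure for this population, and Operations Manual Section 4.1 requires the event behind a fatal outcome to be recorded. The AE-window diagrams in Section 3.3 and Operations Manual Section 4.1 are not reproduced in the text available, so nothing is claimed about them.

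**Conclusion.** The point holds as a modest, inexpensive improvement. For subjects dosed in this study whose End of Treatment falls at day 42 ± 3, 25 to 31 days at the end of the AE window have no scheduled contact before it closes, apart from the Step 5 exceptions. The 36% to 44% range is a share of the post-last-dose period only. A reader might take it as a share of the whole AE window, but that window starts at first dose or enrollment, and for a two-dose retreatment with End of Treatment at day 42 the share is 25%.

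AEs after End of Treatment are collected late and may be under-captured. A reader might infer that the disclosed AE rate is biased downward. The documents do not show this: later visits ask about the same period, and nothing in the plan lets the loss be measured. Under-capture is a risk of unknown size.

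For survival follow-up, the finding is an inconsistency. Section 5.6 and Operations Manual Section 2.3 give different intervals, the latter has no stated anchor, and the passages must be reconciled.

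**What to change.** 1. In Section 5.6, make the day-70 safety phone contact (for example day 70 + 7 days) required for every subject dosed in this study unless consent is withdrawn. State that it collects new as well as ongoing AEs, SAEs and concomitant medication through day 70, with onset dates.
2. Add it as a column in Appendix D for Arm B and retreatment, and as a visit in Operations Manual Section 2.3. A visit already due on days 70 to 77 could serve instead.
3. Reconcile the survival follow-up interval between Section 5.6 and Operations Manual Section 2.3, and state the date from which it is counted.

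The cost is one phone call per treated subject, a small addition to site workload, and a few lines of text. The protocol already contemplates the call, and treatment does not change.
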